The NCEH laboratory will perform the analyses of serum PFAS according to the biochemical analytical plan (Attachment 2) and approved laboratory methods (Kuklenyik 2015). The NCEH laboratory staff will also aliquot and ship blood and serum specimens to participating laboratories for the analyses of the effect biomarkers according to the plan. The recipient will store the urine samples and conduct analyses at a later date when more knowledge is gained about urinary PFAS and effect biomarkers and until the laboratory methods are developed. Residual blood and urines will be archived at NCEH so that additional PFAS or effect biomarkers can be analyzed as new knowledge and analytical methods become available.

23 3.6.5 Questionnaire

Each adult participant, and a parent of the child participant, will complete a questionnaire during theappointment for the blood draw.

26 3.6.5.1 Children and Parents

27 Study staff will request that the parents of the child participant complete the questionnaire. The 28 questionnaire will obtain demographic information (e.g., education, primary occupation), residential history, water consumption habits, medical history of the mother and child, the child's medications, the mother's reproductive history (including maternal age at birth of the participating child) and any occupational exposures the mother may have had to PFAS. The questionnaire will be administered in two formats: a form for the child whose parent is not also a participant (Attachment 15), and an abbreviated form for the child whose parent is also an adult participant (Attachment 15a).

6 The questionnaire will obtain the mother's and child's residential history in the study area, and the dates 7 and length of time of the pregnancy and breastfeeding of the child. The questionnaire will also obtain 8 information on the water consumption habits (including use of water for formula, juices, etc., bottled 9 water use) of the mother and child when they resided in the study area. Information on the mother's 10 workplaces in the study area (location and dates) and the child's daycare and schools in the study area 11 (location and dates) will be obtained.

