 the source via ground water, then the recipient should seek information on the extent of the
 contamination plume from the state environmental agency, EPA, and/or the industrial facility.

If the contaminated drinking water is from a municipal system, then the characteristics of the distribution system will be obtained from the water purveyor. If supply wells are used, then the recipient will request historical and current information on these wells including monthly or daily production logs and dates of operation. If a surface water source is used or if water is purchased from another purveyor, then the recipient will request information about this source.

10 The recipient will also request the results of all relevant PFAS sampling: in the surface water near the 11 drinking water intakes, in the distribution system, in the supply wells and nearby monitoring wells, in 12 purchased water from other water purveyors, and in the private wells in the study area.

13

14 **3.10 Statistical Analyses**

15 ATSDR staff will perform statistical analyses with the participation of the recipients using SAS, R and STATA 16 on the combined multi-site study dataset. ATSDR staff may also use SPSS for data management. ATSDR 17 staff will calculate descriptive statistics (including means, geometric means, medians, standard deviations, 18 and percentiles) to identify the presence and distribution of PFAS and effect biomarker analytes. Statistical 19 methods will include multiple linear regression of continuous (untransformed and natural log transformed) effect biomarkers on continuous (untransformed and natural log transformed) PFAS serum 20 21 levels and categorized PFAS serum levels, and logistic regression of categorized effect biomarkers (e.g., 22 hypercholesterolemia) or disease prevalence on continuous (untransformed and natural log transformed) 23 and categorical PFAS serum levels. ATSDR staff will use restricted cubic spline methods (or generalized 24 additive models using cubic regression splines) for linear and logistic regression to obtain flexible, 25 smoothed exposure-response curves. To identify risk factors that may act as confounders for a particular health outcome, the analysis will implement a "10% change in the estimate" rule (Maldonado 1993). 26

Primary analyses will focus on estimated cumulative PFAS serum levels. Supplemental analyses will
evaluate PFAS serum levels in the blood specimens obtained in the study as well as estimated maximum

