Section B: Residential History and Drinking Water Exposures

This next set of questions is about the child and the child's birth mother. If you are not her, we can follow up after this interview with a quick phone call to complete the questionnaire.

B1. What is the main source of tap water in your home?

____Public water system

____Private well

____Other: specify _____

____Don't know

_____Refused to answer

B2. On average, how many 8 oz. cups of tap water or beverages prepared with tap water does your child currently drink per day at home?

____ cups

____Doesn't drink tap water

____Don't know

____Refused to answer

Note: 1 cup = 8 oz.; 2 cups = 1 pint (16 oz.); 4 cups = 1 quart (32 oz.); 16 cups = 1 Gallon (128 oz.

B3. On average, how many 8 oz. cups of tap water or beverages prepared with tap water do you currently drink per day at home?

____ cups

____Doesn't drink tap water

____Don't know

Refused to answer

Note: 1 cup = 8 oz.; 2 cups = 1 pint (16 oz.); 4 cups = 1 quart (32 oz.); 16 cups = 1 Gallon (128 oz.

B4. What was your previous address?

Street	Apt	
City	State	Zip Code:

B5. When did you move into your previous address? Month____ Year_____

B6. What was the main source of tap water at that address?

____Public water system

____Private well

____Other: specify _____

____Don't know

_____Refused to answer

B7. On average, how many 8 oz. cups of tap water or beverages prepared with tap water did your child drink per day when living at your previous address?

____ cups

_Don't drink tap water

Don't know

____Refused to answer

____Your child did not live at this address

Note: 1 cup = 8 oz.; 2 cups = 1 pint (16 oz.); 4 cups = 1 quart (32 oz.); 16 cups = 1 Gallon (128 oz.

B8. Have you or your child lived at any other address since January 2000?

___Yes

__No → go to Section C

____Don't know \rightarrow go to Section C

____Refused to answer \rightarrow go to Section C

B9. Please fill out the table below for these other residences where you or your child lived since January 2000.

Street Address, City, State	Did your	Your child's average	Move in	Main source of
	child live	consumption of tap	(mm/yy)	tap water at
	at this	water per day (# cups)		this address
	address?	at this address		(public water
				system or
				private well?)

Note: 1 cup = 8 oz.; 2 cups = 1 pint (16 oz.); 4 cups = 1 quart (32 oz.); 16 cups = 1 Gallon (128 oz.

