Section B: Residential History and Drinking Water Exposures

B1. On average, how many 8 oz. cups of tap water or beverages prepared with tap water does your child currently drink per day at home?

____ cups

____Didn't drink tap water

____Don't know

____Refused to answer

Note: 1 cup = 8 oz.; 2 cups = 1 pint (16 oz.); 4 cups = 1 quart (32 oz.); 16 cups = 1 Gallon (128 oz.)

B2. Please fill out the table below for all residences that your child has lived.

Street Address, City, State	Your child's	Move in	Main source of
	average	(mm/yy)	tap water at
	consumption of		this address
	tap water per		(public water
	day (# cups) at		system or
	this address		private well?)

B3. When [you were/the child's birth mother was] pregnant with your child, on average how many 8

oz. cups of tap water or beverages prepared with tap water did [you/she] drink per day?

____ cups

___Didn't drink tap water

____Don't know

____Refused to answer

B4. When [you were/the child's birth mother was] breastfeeding your child, on average how many 8

- oz. cups of tap water or beverages prepared with tap water did [you/she] drink per day?
- ____ cups
- ____Didn't drink tap water
- ____Don't know
- ____Refused to answer
- ____Did not breastfeed my child

Section C: History of Potential Exposure Modifiers

This next set of questions is for the child's birth mother about the child. If you are not her, we can follow up after this interview with a quick phone call to complete the questionnaire.

- C1. Has your child ever had a blood transfusion?
- ____Yes ightarrow Please specify how many times your child had a blood transfusion______
- ___No →go to Question C3
- ___Don't know →go to Question C3
- ____Refused to answer →go to Question C3
- C2. When did your child last have a blood transfusion?

_____month/year

- C3. Has your child ever donated blood?
- ____Yes → Please specify how many times your child has donated blood______
- ___No \rightarrow go to Section D.
- ____Don't know \rightarrow go to Section D.
 - ___Refused to answer \rightarrow go to Section D.
- C4. When did your child last donate blood? _____ Month/Year

C5. On average, how often does your child donate blood in a year?

Section D: Occupational History of the Child

This next set of questions is for the child's birth mother about the child. If you are not her, we can follow up after this interview with a quick phone call to complete the questionnaire.

D1. Has your child been employed for at least one month at a job?

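### The long-form child questionnaire never asks when mother and child moved into the current home, a date the primary exposure estimate needs

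*Protocol*

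**What the plan says.** Protocol Section 3.6.5.1 states: "The questionnaire will obtain the mother's and child's residential history in the study area, and the dates". The dates at the end of that extract are those of pregnancy and breastfeeding, so the section promises a residential history without spelling out its fields. Section 3.9 lists the reconstructed concentration in the water the participant drank among the inputs to the exposure model. Section 3.10 states: "Primary analyses will focus on estimated cumulative PFAS serum levels".

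The long form (Attachment 15), Section B, is meant to supply the history:

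- B1 to B3 concern the current home. B1 asks "B1. What is the main source of tap water in your home"; B2 and B3 ask how many cups the child and the respondent drink now. None asks for a date.
- B4 to B7 concern the previous address. The only date is in "B5. When did you move into your previous address". No move-out date is asked.
- B8 asks "Have you or your child lived at any other address since January 2000", and B9 continues "B9. Please fill out the table below for these other residences where you or your child lived since January 2000". The B9 table has a move-in column and no move-out column.

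The short form (Attachment 15a), B2, takes another route: "Please fill out the table below for all residences that your child has lived". That table has a move-in column and does not set the current home apart.

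**The concern.** The move from the previous to the current home marks both the end of exposure at one address and the start at the other, and the long form does not ask for it. If the two homes had different water, the number of years on each supply has to be guessed, and that number drives a cumulative serum estimate directly. No later analysis plan can recover a date that was not collected.

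The mother is affected too. Section G of the long form dates her pregnancies, and B10 and B11 ask how much tap water she drank while pregnant and breastfeeding. Without her move-in date, those amounts cannot always be tied to an address. Section 5 names in utero exposure as something that modelling of historical serum might supply.

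Under Section 3.6.5.1 the long form goes to children whose parent is not also an adult participant. The error would therefore fall on one identifiable part of the child sample and not on the rest.

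**Working it through.** **Step 1. Which dates Section B yields.**

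| Address | Move-in asked | Move-out asked |
|---|---|---|
| Current home (B1–B3) | no | not applicable |
| Previous home (B4–B7) | yes (B5) | no |
| Other homes since January 2000 (B8–B9) | yes | no |

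For consecutive homes, each move-out can be read from the next move-in. The chain breaks at the last link: the previous home's end would come from the current home's start, which is missing.

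**Step 2. Whether another instrument fills the gap.** The screening script (Attachment 4) and the contact form (Attachment 10) ask for addresses but no residence dates. The script's bracketed note on the 15-year exposure window is an instruction still to be worked out, and it concerns how recent the exposure was. Under Section 3.5 the water purveyor is asked for account name and street address. The Manual of Procedures (Attachment 12) is a placeholder. Because the parent is not an adult participant, there is no adult questionnaire from that parent to draw on.

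**Step 3. What the form does pin down.** If B7 says that the child never lived at the previous address, and B9 lists no other home for the child, the date of birth (A3) gives the postnatal start at the current home. The mother's own move-in is then known only to lie between the B5 date and the birth. If the child lived at both homes, B5 is only an earliest bound for the move.

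**Step 4. How much the missing date can matter.** The plan states no figure on this, so the following is an illustration. Assumptions: one compartment, constant intake at the current home from move-in to blood draw, none at the previous home, first-order elimination. Half-lives come from Section 3.2.1: about 3 years (PFOA, PFOS), about 5 years (PFHxS), and 5 to 8 years from the second source cited there.

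Take a visit in 2020, a previous home entered in January 2005, and a child now 12 who lived in both. A move in 2012 (8-year stay) and a move in 2018 (2-year stay) give the same Section B answers.

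With k = ln 2 / half-life and T = years at the current home:

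- cumulative serum ÷ steady-state level = T − (1 − e^(−kT)) / k
- serum at draw ÷ steady-state level = 1 − 2^(−T/half-life)

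For a half-life of 3 years, k = 0.231:

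- T = 8: 8 − 0.8425/0.2310 = 4.35
- T = 2: 2 − 0.3700/0.2310 = 0.398
- ratio: 4.35/0.398 = 10.9

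| Half-life | Cumulative, T = 8 | Cumulative, T = 2 | Ratio | Serum at draw, T = 8 vs T = 2 |
|---|---|---|---|---|
| 3 y | 4.35 | 0.398 | 10.9 | 84% vs 37% |
| 5 y | 3.17 | 0.253 | 12.5 | 67% vs 24% |
| 8 y | 2.23 | 0.164 | 13.6 | 50% vs 16% |

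The modelled cumulative serum from that home differs about 11- to 14-fold between two histories that Section B cannot tell apart.

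**The case against.** The best reply is that this is one missing field and that other data limit the damage. Much of that is fair.

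- Sections E2 and E3 of the same form ask for daycare and school addresses with start and end dates, and D3 asks where and when the mother worked. A move between areas will often show there. A move within one school district, or of a home-schooled child (for whom the school table is skipped), may not.
- Residence dates are one input among several. Section 3.9 also uses measured serum, NHANES background levels and pharmacokinetic modelling. In the illustration, serum at draw differs only about 2.3-fold (0.84/0.37) to 3.1-fold (0.50/0.16), and the measured value helps to separate the two histories. But Section 5 offers reconstruction as a way to limit reverse causation from concurrent measurement. The more the duration is inferred from the measured level, the less the reconstruction serves that purpose.
- The 11- to 14-fold range assumes a clean previous home. For a move within one uniformly contaminated system, the date matters little.
- Only long-form children are affected. The protocol does not say how many there will be, and it expects some parents to join both studies.

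A reader might also infer from B8, B9 and D3 that the mother's history stops at January 2000 and that her earlier exposure is lost, most of all for the oldest children. The form does not support that. It asks about homes and jobs held since that date but records when each began, and B4 and B5 have no cut-off. A home occupied from 1988 to 2003 would be listed with its 1988 start. Only homes and jobs that ended before 2000 are omitted. Nor does the eligibility rule call for a period counted back from the child's birth, since its 15 years run back from the start of the study.

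**Conclusion.** The gap is real and can be confirmed item by item: the long form does not record the move from the previous to the current home, and nothing else in the document asks for it directly. It affects long-form children who lived at both addresses, and the mother's prenatal exposure at the current home even where the child's own start is known from the date of birth.

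It would be too strong to say that exposure at the study address cannot be dated at all. For some children it can be dated or bracketed from A3 with B7, or from E2 and E3. The 11- to 14-fold range shows what the Section B answers permit under the stated assumptions; it is not an expected average error. The number of children affected cannot be derived from the document.

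Within those limits, the form falls short of the residential history promised in Section 3.6.5.1 and of what the primary exposure in Section 3.10 needs. It should be corrected before it is used.

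**What to change.** In Attachment 15, Section B, ask month and year of move-in to the current home, separately for mother and child, and add move-out dates for the previous and other addresses. Alternatively, replace B4 to B9 with a single table of all residences, including the current one, with columns for move-in, move-out, who lived there, water source and cups per day. This would bring the long form into line with B2 of the short form.

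Extending the January 2000 cut-off for the mother's earlier homes and jobs is optional and not needed to close this gap.

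The cost is about a minute more on a form estimated at 30 minutes, with no added participants, visits or procedures. The form still carries a placeholder OMB number, so the wording can be changed now. After fieldwork, the same date would have to be obtained by recontacting families.

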B10. When [you were/the child's birth mother was] pregnant with your child, on average how many 8 oz. cups of tap water or beverages prepared with tap water did [you/she] drink per day?

____ cups

____Didn't drink tap water

____Don't know

____Refused to answer

B11. When [you were//the child's birth mother was] breastfeeding your child, on average how many 8 oz. cups of tap water or beverages prepared with tap water did [you/she] drink per day?

- cups
- ____Didn't drink tap water
- ____Don't know
- ____Refused to answer
- ____Did not breastfeed my child

Section C: History of Potential Exposure Modifiers

This next set of questions is about the child and the child's birth mother. If you are not her, we can follow up after this interview with a quick phone call to complete the questionnaire.

- C1. [Have you/Has the birth mother] ever had a blood transfusion?
- ____Yes → Please specify how many times you had a blood transfusion______
- ___No →go to Question C3
- ____Don't know →go to Question C3
- ____Refused to answer →go to Question C3
- C2. When did [you/she] last have a blood transfusion? month/year
- C3. Has your child ever had a blood transfusion?
- ____Yes ightarrow Please specify how many times your child had a blood transfusion______
- ___No →go to Question C5
- ____Don't know →go to Question C5
- ____Refused to answer →go to Question C5
- C4. When did your child last have a blood transfusion?
- _____month/year
- C5. [Have you/Has the birth mother] ever donated blood?

___Yes

___No →go to Question C8

- ____Don't know →go to Question C8
- ____Refused to answer →go to Question C8
- C6. When did [you/the birth mother] last donate blood? _____ Month/Year

C7. On average, how often [do you/does the birth mother] donate blood in a year?

- C8. Has your child ever donated blood?
- ____Yes → Please specify how many times your child has donated blood______
- ___No \rightarrow go to Question D1.
- ____Don't know \rightarrow go to Question D1.
- ____Refused to answer \rightarrow go to Question D1.
- C9. When did your child last donate blood?
- _____ Month/Year

C10. On average, how often does your child donate blood in a year?

_____times

Section D: Occupational History

This next set of questions is about the child's birth mother. If you are not her, we can follow up after this interview with a quick phone call to complete the questionnaire.

D1. What is [your/the child's birth mother's] primary occupation?

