D2. On average, how many 8 oz. cups of tap water or beverages prepared with tap water do you currently drink per day at work?

____ cups

- ____Don't drink tap water
- ____Don't know
- ____Refused to answer

D3. Please fill out the table below for each job that lasted one month or more starting from the present and working back to 2000.

Job information	Job 1	Job 2	Job 3	Job 4
a. Where did the child's mother work				
(City, State)				
b. Name of the employer				
c. Start date (month, year)				
d. End date (month, year)				
e. Job title/description				
f. Did the child's mother work as a	Yes	Yes	Yes	Yes
firefighter?	No go to question g.	No go to question g.	No go to question g.	No go to question g.
If the child's mother worked as a	Yes	Yes	Yes	Yes
firefighter, did she come into contact	No	No	No	No
with firefighting foam used for fires	Don't know	Don't know	Don't know	Don't know
that involve flammable liquids (also				
known as class B fires)?				
g. was this job in any of the following	Manufacturing of nonstick	Manufacturing of nonstick	Manufacturing of nonstick	
Industries?	cookware	cookware	COOKWARE	COOKWARE
	yes no	yesno	yesno	yes10
	Manufacturing of stain resistant	contings used on cornets	contings used on cornets	contings used on carpots
	coatings used on carpets,	unbolstony and other fabrics	upholstony and other fabrics	upholstory, and other fabrics
	uphoistery, and other fabrics	ves no	ves no	
	yes10	Manufacturing of water resistant	Manufacturing of water resistant	Manufacturing of water resistant
	clothing	clothing	clothing	clothing
	yes no	yesno	yesno	yesno
h. Did the child's mother work with or		Yes (Please	Yes (Please	Yes (Please specify the chemical)
around any chemicals at this job such	Yes (Please specify the chemical)	specify the chemical)	specify the chemical)	
as solvents, metals, asbestos, or				No
pesticides?	No	No	No	Don't know
	Don't know	n't know	Don't know	
i. Did the child's mother work with	Yes	Yes	Yes	Yes
radiation?	No	No	No	No

Job information	Job 5	Job 6	Job 7	Job 8
a. Where did the child's mother work				
(City, State)				
b. Name of the employer				
c. Start date (month, year)				
d. End date (month, year)				
e. Job title/description				
f. Did child's mother work as a	Yes	Yes	Yes	Yes
firefighter?	No go to question g.	No go to question g.	No go to question g.	No go to question g.
If child's mother worked as a				
firefighter, did she come into contact	Yes	Yes	Yes	Yes
with firefighting foam used for fires	No	No	No	No

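### The long child questionnaire records no maternal tap-water intake for homes or jobs before the pregnancy, so modelled in utero serum for these children rests on an assumed intake

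*Protocol*

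**What the plan says.** Section 3.6.5.1 of the protocol describes what the child questionnaire is to collect. It includes residential history and the water consumption habits "of the mother and child when they resided in the study area". The same section assigns the long form to children whose parent is not also an adult participant.

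On the long form (Attachment 15, Sections B and D), intake is asked as follows.

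- **Respondent, present:** B3 asks how many cups "do you currently drink per day at home"; D2 asks the same for cups "do you currently drink per day at work".
- **Mother, pregnancy and breastfeeding:** B10 asks her average cups per day during the pregnancy. B11 asks about the time when she was "breastfeeding your child, on average how many 8 oz. cups of tap water" she drank.
- **Previous address:** B7 asks only how many cups "did your child drink per day when living at your previous address", and one answer option is that the child did not live there.
- **Other addresses:** B9 reads "Please fill out the table below for these other residences where you or your child lived since January 2000". It therefore lists homes where the mother lived without the child, yet its only intake column is for the child.
- **Mother's jobs:** D3 goes back to 2000 with place, employer and dates, but has no water item.

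The child's daycare and school tables (E2, E3) do ask cups per day for each place.

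Section 3.9 lists questionnaire data on water consumption among the inputs to the estimated cumulative serum level. Section 3.10 makes that estimate the basis of the primary analyses. Section 3.2.1 admits children exposed in utero or during breastfeeding. Section 5 says that modelling might make it possible to estimate exposure in critical periods, with in utero exposure as the example.

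**The concern.** The form is narrower than the section that describes it. PFAS build up over years, so the mother's serum when she conceives reflects what she drank before the pregnancy. For that period the form asks where she lived and worked, but not how much she drank. Where the child was not yet born, the child's cups in B7 and B9 are blank or not applicable.

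For these children no adult questionnaire stands behind the form, since it is issued when the parent is not an adult participant. A statistical analysis plan can choose an assumption for the missing intake but cannot supply the answer. What is at stake is the accuracy of individual in utero estimates, and of the early part of the reconstructed child serum that depends on them.

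**Working it through.** The plan gives no figure on this point, so there is none to reproduce. The check has two parts.

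**1. Coverage of the mother's intake on the long form**

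| Period or place | Her cups asked? | Item |
|---|---|---|
| Present, home | yes, as the respondent | B3 |
| Present, work | yes, as the respondent | D2 |
| Pregnancy | yes | B10 |
| Breastfeeding | yes | B11 |
| Previous address | no, child only | B7 |
| Other addresses since January 2000 | no, child only | B9 |
| Earlier jobs since 2000 | no | D3 |
| Current home before the pregnancy | no | none |

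B3 and D2 address the person answering, who need not be the birth mother. No item in Section B asks when the family moved into the current home.

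**2. How much the missing period matters**

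Inputs: half-lives T of about 3 years (PFOA, PFOS) and 5 years (PFHxS), and an upper value of 8 years from the 5 to 8 year range, all in Section 3.2.1. Assumptions: one compartment with first-order elimination, k = ln 2 / T; pregnancy of 0.75 years; steady state at conception; drinking-water part of serum only.

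- Share of serum at delivery from intake before conception: exp(−0.75k) = 2^(−0.75/T).
- The same share averaged over pregnancy: a = (1 − exp(−0.75k)) / (0.75k).
- If B10 is carried back and true earlier intake is r times B10, true over modelled average in utero serum = r·a + (1 − a).

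| T (years) | Share at delivery | Average share a | r = 0.5 | r = 2 |
|---|---|---|---|---|
| 3 | 0.841 | 0.918 | 0.54 | 1.92 |
| 5 | 0.901 | 0.950 | 0.53 | 1.95 |
| 8 | 0.937 | 0.968 | 0.52 | 1.97 |

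Intake during pregnancy, the part B10 measures directly, therefore accounts for 1 − a, or about 3% to 8% of the average. The values r = 0.5 and r = 2 are illustrations; the documents do not say how far intake changes around a pregnancy.

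**What an added column would recover.** B9 and D3 start in January 2000. With U years from then to conception, the share of delivery serum falling inside the tables is 2^(−0.75/T) × (1 − 2^(−U/T)). Assume births from 2002 to 2015.

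- 2002 birth, U = 2002 − 0.75 − 2000 = 1.25: 0.841 × 0.251 = 21% at T = 3; 0.937 × 0.103 = 10% at T = 8.
- Mid-range birth, U = 2008.5 − 0.75 − 2000 = 7.75: 0.841 × 0.833 = 70% at T = 3; 0.937 × 0.489 = 46% at T = 8.

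**The case against.** A reader might infer that in utero exposure cannot be modelled at all for these children. The documents do not support that. The long form records the mother's earlier addresses with move-in dates and water source, her jobs with dates, the dates of pregnancy and breastfeeding, and her intake in pregnancy. Section 3.9 adds reconstructed water concentrations, NHANES background levels and pharmacokinetic models. A model with B10 carried back, or with a default intake, can be run.

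Nor is 84% to 94% the share left unmeasured or the size of the error. It is the share of serum accrued before conception at steady state. Place, time and water source are known for much of that period; only the cups are missing. Where the mother's intake was stable, or she had little contaminated water before the pregnancy, the error is small.

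The data are not lost for good either. The contact form (Attachment 10) foresees calling participants back with clarifying questions, and Section B provides for a follow-up call when the respondent is not the birth mother.

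Section 2.2 also shows a modest contrast by water intake: geometric mean PFHxS of 4.76 against 3.77 µg/L for 4 or more cups a day against fewer, a ratio of 1.26. This compares two broad groups on total serum, background included. It does not bound the error for one mother, but it warns against reading the 0.5 and 2 examples as expected errors in total serum.

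Finally, recalled cups at addresses up to two decades back are weak data, and nothing here shows how far they would beat carrying B10 back. That is a fair reservation. But the form already relies on such recall in B10 and B11, and for the child in B7 and B9.

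**Conclusion.** The gap is real and contradicts Section 3.6.5.1. For long-form children the mother's pre-pregnancy intake has to be assumed, and an error in that assumption passes almost in proportion into the drinking-water part of modelled in utero serum: about 0.52 to 0.54 times the modelled value if true earlier intake was half of B10, and 1.92 to 1.97 times if it was double. This rests on first-order kinetics, steady state at conception and half-lives of 3 to 8 years.

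The consequence is an untested assumption in place of an individual answer. It is not a failure of the reconstruction, and Section 5 presents in utero estimation only as a possibility. The number of children affected is unknown, because the split between long and short forms is not given. The adult questionnaire (Attachment 16) is not in the text at hand, so nothing is claimed about mothers who complete it. The change is cheap and best made before the form is used, since re-contact later would cost more.

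**What to change.** In Attachment 15, long form:

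- Add to B9 a column for the birth mother's average cups of tap water per day at each address.
- Add the matching question for her beside B7.
- Add to D3 a row for her cups of tap water per day at each job.
- Ask her pre-pregnancy intake at the current home if she already lived there, with the move-in date that this requires.
- Word all of these for the birth mother, not for the respondent.

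The cost is about 1 to 2 minutes on a form estimated at 30 minutes, plus recall error in the new answers. Because the tables start in January 2000, the change recovers only part of the pre-conception share for the oldest children: about 10% to 21% of delivery serum for 2002 births, against 46% to 70% at mid-range. Intake before 2000 would still have to be assumed.
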